6.7.1 Definition of clinical malaria

A clinical episode of *P. falciparum* malaria is defined as the presence of *P. falciparum* asexual parasitemia on Giemsa-stained thick blood smear films in the presence of the following: (i) fever defined as oral temperature $\geq 37.5^{\circ}$ C in the absence of other evident clinical conditions that could explain the fever; and/or (ii) one or more of the following symptoms consistent with malaria including but not limited to headache, vomiting, abdominal pain, or myalgia with or without fever. This case definition is based on seven continuous years of clinical experience treating children and adults with malaria in Bandiagara, and represents the current standard for clinical decisions to treat malaria in this setting. Study investigators will use their best clinical judgment in deciding when to treat malaria and will not be precluded from treating malaria by this definition.

Page 35 of 96 Version 17, DEAP/MRTC/MMVDU CONFIDENTIAL

7 CONDUCT OF THE STUDY

Detailed SOPs will be used for the study procedures described in this section. Staff and investigators will be trained in the SOPs relevant to their duties and sign copies of the SOPs to document this training. Copies of SOPs will be available for inspection and review by the DMID, USAMMDA, GSKBio, WRAIR and study monitors. The general methods that will be used are summarized in the following sections.

7.1 General study aspects

7.1.1 Screening and inclusion process

Recruitment will be progressive until 60 adults of either gender who fulfill the inclusion criteria are included in the study. Volunteers will be recruited by non-coercive methods among adults 18-55 years of age residing in Bandiagara. They will be recruited after coming voluntarily to the BMP clinic. No undue influence will be exerted upon volunteers to obtain their consent. After the study has been explained to the potential volunteers, they will be allowed to leave and return later with their decision; this will allow time for them to discuss the study with their family and carefully consider their involvement in the study. Finally, at the BMP clinic, the individual consent process will be conducted in a separate and private room to ensure confidentiality, to reduce the likelihood of other participants influencing the decision to participate, and to allow further time to make a final decision.

After community information is disseminated as described in Section 15.2.1, all interested and potentially eligible adults aged 18-55 will be invited to visit the study clinic on a specific date. These individuals will receive oral and written explanation of the study, after which screening consent will be obtained from those willing to participate. All screening tests, medical history and examinations will be performed only after screening consent is obtained. Women who express unwillingness to avoid pregnancy will be excluded from the remainder of the screening process. Any clinically relevant finding that is discovered upon screening will either be treated appropriately by study clinicians or referred for more comprehensive diagnosis and treatment at the government health clinic. Study clinicians will generally handle acute, simple conditions such as malaria or other acute infections. More complicated or chronic conditions, such as chronic renal or heart disease, will be referred to appropriate sources of medical care.

Upon screening, the Investigator will prepare a screening form for each participant. This screening form will later become part of the CRF for participants enrolled in the vaccine trial. A unique screening identification number will be assigned to each study participant. Participants will provide a medical history, with special attention to any history of recurrent infections to suggest immune suppression, previous history of splenectomy and prior vaccine reactions. They will also undergo physical examination and laboratory screening tests, which include (see section 8.2 for details on laboratory testing to be performed): complete blood count (CBC) creatinine, ALT, urine dipstick analysis, and urine β -HCG (for females to exclude pregnancy). Urine β -HCG will be obtained on female participants just before each immunization. A participant who meets any of the exclusion criteria will be managed initially by study clinicians and referred to the local health center for evaluation as necessary. All screening tests will be completed within the 35 days prior to entry into the study. Laboratory studies may be conducted at other times

Page 36 of 96 Version 17, DEAP/MRTC/MMVDU CONFIDENTIAL

during the course of the trial if the investigators judge it necessary for the safety of the participant. All screening and follow-up diagnostic laboratory testing will be performed at the Bandiagara Malaria Project laboratory in Bandiagara and if applicable at the MRTC clinical laboratory in Bamako. Recruitment will continue until 60 eligible participants have fulfilled all of the inclusion criteria and none of the exclusion criteria, and signed the study consent form. Should participants change their mind and decline to participate prior to immunization, additional participants will be screened until 60 participants are enrolled. Each study subject will receive a photo ID card and a copy of the photo ID will be attached to the CRF folder for each participant.

7.1.2 Treatment allocation and randomization

Individual participants will be randomized to receive either full dose or half dose FMP2.1 or RabAvert[®] Rabies vaccine without stratification for gender. Participants will be randomized to two groups of 30 subjects (cohorts 1 and 2). The first 30 eligible volunteers will constitute the first cohort and will be randomized in a 2:1 ratio to receive 25µg of FMP2.1 adjuvanted with 0.25 mL of AS02A (n=20) or RabAvert[®] vaccine (n=10). Similarly, the next 30 eligible volunteers will constitute the second cohort (cohort 2) and will be randomized in a 2:1 ratio to receive 50ug of FMP2.1 adjuvanted with 0.50 mL of AS02A (n=20) or RabAvert® vaccine (n=10). Within each cohort, treatments will be assigned to subject ID numbers in randomized blocks. Randomization to either the two vaccines (FMP2.1/AS02A or RabAvert®) will be done using a computer-generated randomization list. The randomization list will contain sequential codes linking a study number to a vaccine assignment (FMP2.1/AS02A or RabAvert®). Study numbers will be assigned to participants of each cohort in the order in which they provide written informed consent to be enrolled in the vaccine trial. The vaccine and dose that are assigned during the first immunization will be maintained for second and third immunizations. Access to the randomization list will be exclusively limited to the study drug manager(s)/pharmacist(s), study statistician in Bamako, and statistical consultant in Baltimore. These individuals are unblinded and will not be involved in study participants' further evaluation. The Local Medical Monitor will also keep one set of the randomization code in a sealed envelope, in the event that emergency unblinding is required. The reason for any unblinding will be documented as well as the steps taken.

7.1.3 Vaccination process

Before each vaccination, criteria for continued eligibility will be reviewed and verified. The volunteer participation will be pursued only if she or he is deemed eligible to receive vaccination. A history-directed physical examination will be done and oral temperature, blood pressure, pulse and baseline general symptoms will be recorded. Venous blood will be collected for laboratory analysis and urine will be collected from female volunteers and tested for β -hCG by dipstick testing.

After the participant's identity is checked by comparing his/her photo ID and study number with that on the CRF, he/she will be vaccinated by intramuscular injection into the left deltoid muscle. If any local impairment prevents administration of the vaccine into the upper arm for that particular immunization, the vaccine may be administered into the opposite arm in the
Page 37 of 96 Version 17, DEAP/MRTC/MMVDU CONFIDENTIAL

deltoid region (see section 9.2.3). Vaccination will be done on study days 0, 30 ± 7 and 60 ± 7 . Double blinding will be maintained as described in detail in Section 9.4.

7.1.4 Post-immunization evaluations

After immunization, the participant will be observed for onset of local and systemic reactions. The participant will be observed for a minimum of 30 minutes post-vaccination. Signs and symptoms (as detailed in Section 10) will be solicited and recorded by the investigators according to adverse events recording procedures (see Section 10).

Participants will complete a 7-day surveillance after each vaccination at the BMP clinic center (including day 0, the day of vaccination). All adverse events occurring during this 7-day period will be followed until resolution or stabilization. If any symptom persists beyond the 7-day surveillance period the participant will be followed daily until resolution of the adverse event.

After the 7-day surveillance period, participants will be asked to come to the BMP clinic center on days 14 +/- 3 and 30 +/- 7 after vaccination. At each visit, a study physician will evaluate the participants. A complete clinical examination will be performed and information on any solicited or unsolicited symptoms since the last visit will be collected. Every effort will be made to ensure compliance with visits. Local guides will conduct home visits to participants a day before their scheduled visit at the clinic. If a participant does not appear for a scheduled clinic visit, the local guide will visit him/her again and accompany the participant to the clinic center. If a serious adverse event (SAE) has occurred, appropriate measures will be taken to notify the PI, Local Medical Monitor, SMC, and all sponsors and IRBs as described in section 10.5.2.

7.1.5 Dose escalation

As soon as possible after the completion of the 7-day surveillance period following each immunization with the 25 μ g dose of FMP2.1, the PI, Local Medical Monitor, at least two members of the SMC, and the Study Co-Sponsor (DMID) will review safety results and decide whether to proceed with next scheduled immunization with the full dose. Ultimately, the decision to proceed with each dose escalation will be made by the Study Co-Sponsor based on advice from the Local Medical Monitor and SMC and in consultation with WRAIR, GSKBio and investigators as described in detail in Section 15.4

7.1.6 Detailed description of study visits

Day -35 to -1 Screening /inclusion of participants

Meetings will be held with town administrative and medical authorities to explain the purpose of the study. These will be followed by meetings with the traditional authorities and the heads of families for village-level "permission to enter." Subsequently, general information about the study will be disseminated through the local radio station. The target population will be invited for screening as described in investigator's subject recruiting SOPs. Screening will be performed until 60 volunteers are included.

Visit 1 (may take place over more than one visit)

Page 38 of 96 Version 17, DEAP/MRTC/MMVDU CONFIDENTIAL

- Written informed consent for screening
- Medical history of participant
- Complete physical examination
- Collect 5-10 mL venous blood sample to measure:
 - Hematology: Complete Blood Count (CBC) which includes: red blood cells, platelets, white blood cell count, lymphocyte count, hemoglobin, mean corpuscular volume and mean corpuscular hemoglobin concentration.
 - Biochemistry: serum creatinine and ALT
- Beta-HCG pregnancy test on urine for females •
- Collect urine: dipstick for blood, glucose and protein.
- Check of inclusion and exclusion criteria
- Written informed study consent for vaccination
- Assignment of unique study number
- Prepare an ID card containing participant's unique study number and photo for enrolled participants.

Day 0:

Visit 2

Vaccination 1

- Before vaccination:
- Review screening laboratory test results
- Review inclusion/exclusion criteria and check of contraindications/precautions
- Record any complaints, symptom-directed physical examination, and examination of the immunization arm(s) for any abnormalities.
- Record vital signs: oral temperature, blood pressure, pulse
- Record baseline data for solicited general symptoms
- Collect 30-40 mL venous blood sample to measure:
 - CBC, hemoglobin electrophoresis, creatinine, ALT
 - Serum for anti-AMA1 antibody titer and GIA
 - WBC for CMI to AMA1 _
- Collect urine for β-HCG test for females
- Administer study immunization 1 •

After vaccination:

- Observe for a minimum of 30 minutes
- Record blood pressure, pulse, oral temperature
- Record solicited and unsolicited events
- Instruct participants to return to the BMP clinic center immediately should they manifest any signs or symptoms they perceive as serious.

Days 1-3: First 3 days post-vaccination 1 surveillance visits Visit 3-5

- Record vital signs; blood pressure, pulse, oral temperature
- Examine site of injection
- Record solicited and unsolicited signs/symptoms

Page 39 of 96 Version 17, DEAP/MRTC/MMVDU CONFIDENTIAL

• Targeted physical examination including immunization arm(s)

Day 7± 1 day:7 days post-vaccination 1 surveillance visitVisit 6

- Brief medical history
- Record vital signs; blood pressure, pulse, oral temperature
- Physical examination
- Record any unsolicited adverse events occurring after the last study immunization
- Collect 5-10 mL of venous blood to measure CBC, creatinine and ALT

Day 14± 3 days: 14 days post-vaccination 1 surveillance visit Visit 7

- Brief medical history
- Record vital signs; blood pressure, pulse, oral temperature
- Physical examination
- Record any unsolicited adverse events occurring after the last study immunization
- Collect 30-40 mL of venous blood to measure:
 - Serum for anti-AMA1 antibodies and GIA
 - WBC for CMI

Day 30± 7 days:1 month post-vaccination 1 surveillance visit and vaccination 2Visit 8

Before vaccination:

- Check participant's ID to confirm identity
- Targeted physical examination including immunization arm(s)
- Check of contraindications/precautions
- Record vital signs: oral temperature, blood pressure, pulse
- Review medical history and record any unsolicited adverse events occurring since last visit
- Record baseline data for solicited general symptoms
- Collect 30-40 mL venous blood sample to measure:
 - CBC, creatinine, ALT
 - Serum for anti-AMA1 antibody titer and GIA
 - WBC for CMI
- Collect urine for β-HCG test for females
- Administer study immunization 2

After vaccination:

- Observe for at least 30 minutes
- Record blood pressure, pulse, oral temperature
- Record solicited and unsolicited adverse events
- Instruct participants to return to the BMP clinic center immediately should they manifest any signs or symptoms they perceive as serious.

Days 31-33: Days 1,2,3 post-vaccination 2 surveillance visits

Page 40 of 96 Version 17, DEAP/MRTC/MMVDU CONFIDENTIAL

Visits 9-11

- Record vital signs; blood pressure, pulse, oral temperature
- Examine site of injection
- Record daily solicited and unsolicited signs/symptoms
- Targeted physical examination including immunization arm(s)

Day 37 ± 7 days: Day 7 post-vaccination 2 surveillance visit Visit 12

- Record vital signs; blood pressure, pulse, oral temperature
- Examine site of injection
- Record daily solicited and unsolicited signs/symptoms
- Targeted physical examination including immunization arm(s)
- Collect 5-10 mL of venous blood to measure CBC, creatinine and ALT

14 days post-vaccination 2 surveillance visit

Day 44± 7 days: Visit 13

- Brief medical history
- Record vital signs; blood pressure, pulse, oral temperature
- Physical examination
- Record any unsolicited adverse events occurring after the last study immunization
- Collect 30-40 mL of venous blood to measure:
 - Serum for anti-AMA1 antibodies and GIA
 - WBC for CMI

Day 60± 7 days:1 month Post-vaccination 2 surveillance visit and vaccination 3Visit 14

Before vaccination:

- Check participant's ID to confirm identity
- Targeted physical examination including immunization arm(s)
- Check of contraindications/precautions
- Record vital signs: oral temperature, blood pressure, pulse
- Review medical history and record any unsolicited adverse events occurring since last visit
- Record baseline data for solicited general symptoms
- Collect 30-40 mL venous blood sample to measure:
 - CBC, creatinine, ALT
 - Serum for anti-AMA1 antibody titer and GIA
 - WBC for CMI
- Collect urine for β-HCG test for females
- Administer study immunization 3

After vaccination:

- Observe for at least 30 minutes
- Record blood pressure, pulse, oral temperature

Page 41 of 96 Version 17, DEAP/MRTC/MMVDU CONFIDENTIAL

- Record solicited and unsolicited adverse events
- Instruct participants to return to the BMP clinic center immediately should they manifest any signs or symptoms they perceive as serious.

Days 61-63: Days 1,2,3 post-vaccination 3 surveillance visits Visit 15-17

- Record vital signs; blood pressure, pulse, oral temperature
- Examine site of injection
- Record daily solicited and unsolicited signs/symptoms
- Targeted physical examination including immunization arm(s)

Day 67 ± 7 days: Day 7 post-vaccination 3 surveillance visit Visit 18

- Record vital signs; blood pressure, pulse, oral temperature
- Examine site of injection
- Record daily solicited and unsolicited signs/symptoms
- Targeted physical examination including immunization arm(s)
- Collect 5-10 mL of venous blood to measure CBC, creatinine and ALT

Day 74± 7 days:14 days Post-vaccination 3 surveillance visitVisit 19

- Brief medical history
- Record vital signs; blood pressure, pulse, oral temperature
- Targeted physical examination including immunization arm(s)
- Record any unsolicited adverse events occurring after the last study immunization
- Collect 30-40 mL of venous blood to measure:
 - Serum for anti-AMA1 antibodies and GIA
 - WBC for CMI

Day 90± 10 days: 30 days Post-vaccination 3 surveillance visit

Visit 20

- Brief medical history
- Record vital signs; blood pressure, pulse, oral temperature
- Targeted physical examination including immunization arm(s)
- Record any unsolicited adverse events occurring since last visit
- Collect 30-40 mL of venous blood to measure:
 - Serum for anti-AMA1 antibodies and GIA
 - WBC for CMI
 - CBC, creatinine and ALT
- Collect urine for β-HCG test for females

Day 120 ± 10 days to Day 364 ± 10 days:

Post-vaccination Safety surveillance period

• From this date, participants will be visited monthly by local guides to confirm their location and to remind them to come to clinic for routine clinical evaluation.

• Participants are invited to continue to attend the BMP clinic any time they are sick.

Day 180± 14 days to Day 364± 14 days:

Post-vaccination Safety surveillance period

Visit 21-23

- From this day participants will be asked to return to BMP clinic center every 3 months ±14 days.
- Brief medical history
- Record vital signs
- Targeted physical examination including immunization arm(s)
- Collect 30-40 mL venous blood to measure:
 - Serum for anti-AMA1 antibodies and GIA
 - WBC for CMI
 - CBC, ALT, creatinine
- Collect urine for β-HCG test for females
- Participants are invited to continue to attend the BMP clinic any time they are sick. A malaria smear will be done whenever symptomatic malaria is suspected.

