2 GLOSSARY OF TERMS

Participant(s): Term used throughout the protocol to denote the enrolled individual(s).

Subject(s): Term equivalent to participant in the protocol.

Local Medical Monitor: An individual medically qualified to assure the responsibilities of the sponsors especially as regards the ethics, clinical safety of a study and the assessment of adverse events. Synonymous with Sponsor's Medical Expert.

Study Monitor: An individual who is responsible for assuring proper conduct of a clinical study at one or more investigational sites.

IND Sponsor: The U.S. Office of the Surgeon General, which holds the IND for the vaccine.

Co-Sponsor: The Division of Microbiology of Infectious Diseases, NIAID, NIH, which is supporting the trial financially and providing regulatory and other oversight.

Sponsor: When the term "sponsor" is used throughout the protocol without referring specifically to either the IND sponsor or Study Co-Sponsor, it is referring to both of these.

Eligible: Qualified for enrolment into the study based upon strict adherence to inclusion/exclusion criteria.

Evaluable: Meeting all eligibility criteria, complying with the procedures defined in the protocol, and, therefore, included in analysis (see Section 12.3 for details on criteria for evaluability).

Reactogenicity: refers to the both the expected and unexpected symptoms and signs that are associated with the administration of a vaccine. These include local reactions such as erythema, induration, and tenderness, as well as systemic reactions such as fever, malaise, myalgias, and arthralgias.

Study day: Each participant's study day will commence on the day of their first immunization, which shall be Study Day 0. Thus different participants (including participants in the same cohort who may be immunized on different days) will have different Study Days.

Solicited symptoms: Symptoms that are identified by direct questioning/observation about specific symptoms.

Unsolicited symptoms: Symptoms that are mentioned spontaneously by participants or in response to general, open-ended questions such as "How have you been feeling?"

Page 13 of 96 Version 17, DEAP/MRTC/MMVDU CONFIDENTIAL

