10.1.2 Surveillance period for adverse events

All adverse events occurring within 30 days following administration of each study immunization will be recorded irrespective of severity or whether or not they are considered vaccination-related.

Solicited adverse events will be elicited for a 7-day surveillance period (day of vaccination and study days 1, 2, 3 and 7 and unsolicited adverse events will be recorded during a 30-day surveillance period. Serious adverse events will be recorded throughout the study.

Instances of death, cancer or congenital abnormality in offspring of a study subject if brought to the attention of the investigator at any time after cessation of study AND suspected by the investigator to be related to study vaccine, will be reported to the sponsors and GSK Biologicals.

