10.1.3 Recording adverse events

At each visit/assessment, the investigator will evaluate all adverse events observed by the investigators or reported by the participant. New adverse events will be recorded in the Adverse Event form within the participant's CRF. Solicited and unsolicited adverse events will be recorded on separate pages of the CRF. The nature of each event, date and time (where appropriate) of onset, outcome, intensity and relationship to vaccination will be established. Any corrective treatment will be recorded in the CRF. As a consistent method of soliciting adverse events, the participant will be asked a non-leading question such as: "Have you felt different in any way since receiving the vaccine or since the last visit?" The investigator will record only those adverse events having occurred within the time frames defined above.

Adverse events already documented in the CRF, *i.e.* at a previous assessment and designated as 'ongoing' will be reviewed at subsequent visits, as necessary. If these have resolved, the documentation in the CRF will be completed, including the date that the adverse event resolved. If an adverse event changes in frequency or intensity during a study period, a new record of the event will be started.

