12.1 Primary endpoints

Occurrence of solicited symptoms during a 7-day surveillance period after vaccination (day of vaccination and study days 1, 2, 3 and 7).

Occurrence of unsolicited symptoms during a 30-day surveillance period after vaccination.

Occurrence of serious adverse events during the study period.

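### The rules for collecting the primary solicited-symptom endpoint conflict (Visit 6 content, Day-7 windows, way of asking), so capture could differ between vaccination 1 and vaccinations 2 and 3

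*Combined protocol and SAP*

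**What the plan says.** **Endpoint.** Section 12.1 names as the first primary endpoint "Occurrence of solicited symptoms during a 7-day surveillance period after vaccination", and lists the day of vaccination and Days 1, 2, 3 and 7. Section 10.1.2 agrees: "Solicited adverse events will be elicited for a 7-day surveillance period (day of vaccination and study days 1, 2, 3 and 7". The Summary applies this after each vaccination. Table 3 marks solicited recording in the Day 7, Day 37 and Day 67 columns. Section 12.5.3 reports solicited symptoms by group and by vaccine administration.

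**Content of the Day-7 visits.** In section 7.1.6, the only adverse-event line for Visit 6 (Day 7 after vaccination 1) is "Record any unsolicited adverse events occurring after the last study immunization". A general physical examination is listed, but no examination of the injection site. Visits 12 and 18, the matching visits after vaccinations 2 and 3, list both solicited and unsolicited recording and an injection-site examination.

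**Windows.** Visit 6 is Day 7 ± 1. The others read "Day 37 ± 7 days: Day 7 post-vaccination 2 surveillance visit Visit 12" and "Day 67 ± 7 days: Day 7 post-vaccination 3 surveillance visit Visit 18". Table 4 counts the 14-day visits (± 3) and the 30-day visits (± 7) from each vaccination. It has no row for any Day-7 visit.

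**Way of asking.** The glossary defines solicited symptoms as "Symptoms that are identified by direct questioning/observation about specific symptoms" and unsolicited ones as "Symptoms that are mentioned spontaneously by participants or in response to general, open-ended questions such as" a question about how the participant has been feeling. Section 10.1.3 then states: "As a consistent method of soliciting adverse events, the participant will be asked a non-leading question such as" one about feeling different since the vaccine or the last visit.

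**The concern.** These are stated rules that disagree with each other, and they govern a primary endpoint. Staff who work from the visit list in 7.1.6 would collect different data from staff who work from Table 3.

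Three things are at stake:

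- **Comparability across vaccinations.** The tabulation in 12.5.3 could set a first vaccination observed on four occasions beside later ones observed on five. It could also set a tightly timed Day-7 visit beside loosely timed ones.
- **Safety review.** Under section 7.1.5, the decision on each 50 µg immunization follows the 7-day surveillance after the corresponding 25 µg immunization. That review needs the Day-7 contact to be complete and on time.
- **Capture overall.** If only an open question is asked, symptoms that depend on the participant's report could be missed in every group.

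A symptom that was not asked about cannot be recovered at analysis.

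**Working it through.** **1. Solicited contacts per vaccination**

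| Source | Vaccination 1 | Vaccination 2 | Vaccination 3 |
|---|---|---|---|
| 10.1.2, 12.1, Table 3 | 0, 1, 2, 3, 7 = 5 | 5 | 5 |
| 7.1.6 read literally | 0, 1, 2, 3 = 4 | 5 | 5 |

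Only the Day-7 contact after vaccination 1 is in dispute. Days 0 to 3 are solicited after every vaccination.

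**2. Where the Day-7 visits may fall**

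- Visit 6: 7 − 1 = 6 to 7 + 1 = 8 days after vaccination 1.
- Visit 12: study days 37 − 7 = 30 to 37 + 7 = 44. With vaccination 2 on Day 30, that is 0 to 14 days after vaccination.
- Visit 18: study days 60 to 74. With vaccination 3 on Day 60, it is again 0 to 14.

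Visit order trims the lower end, because Visits 9 to 11 occupy Days 31 to 33. It does not trim the upper end: Table 4 lets Visit 13 fall up to 14 + 3 = 17 days after vaccination, so a Visit 12 on day 14 is still in sequence. Post-vaccination days 8 to 14 lie outside the 7-day endpoint period.

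**3. Timing of the review**

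Section 6.1 sets at least 14 days between corresponding 25 µg and 50 µg immunizations so that Day-7 laboratory results can be reviewed. Section 15.4 places the SMC calls about two to three weeks after each 25 µg immunization. A Visit 12 or 18 on post-vaccination day 14 falls on the earliest permitted date of the corresponding 50 µg immunization, and possibly after the data are needed. After vaccination 1 the timing is tight enough, but the visit list omits solicited symptoms.

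**4. Way of asking**

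Section 10.1.4 lists 11 solicited items. Four are measured (swelling, erythema, arm motion, fever). The other 11 − 4 = 7 depend on what the participant reports: injection-site pain, chills, nausea, headache, malaise, myalgia and joint pain. For these seven, 10.1.3 and the glossary give opposite instructions.

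**5. Size**

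The plan's only design figure is Table 6, and it reproduces. Pr(0/20) = (1 − p)^20 gives 0.8179, 0.3585, 0.1887 and 0.1216 at p = 0.01, 0.05, 0.08 and 0.10. The printed values are 0.82, 0.36, 0.19 and 0.12.

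The documents give no capture rate. As an illustration only, let s be an assumed share of affected participants whose symptom is recorded. Then Pr(at least one seen among 20) = 1 − (1 − p·s)^20:

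| True rate p | s = 1 | s = 0.75 | s = 0.5 | s = 0.25 |
|---|---|---|---|---|
| 0.05 | 0.64 | 0.53 | 0.40 | 0.22 |
| 0.10 | 0.88 | 0.79 | 0.64 | 0.40 |
| 0.20 | 0.99 | 0.96 | 0.88 | 0.64 |

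This shows what incomplete capture would cost a group of 20. It is not an estimate for this trial.

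**The case against.** The strongest reply is that the intent is clear and only one bullet departs from it. The Summary, 6.1, 10.1.2, 12.1 and Table 3 all call for Day-7 solicited collection, and 7.1.4 requires 7-day surveillance after each vaccination. This stands as far as it goes. A reader might infer that the first Day-7 assessment is lost for all 60 participants. That follows only if staff put the 7.1.6 list above everything else.

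The recall in 7.1.4 is a weaker safeguard. It asks at the 14- and 30-day visits for solicited symptoms since the last visit. At Day 14 that reaches back only to Visit 6, the Visit 7 list again names only unsolicited events, and Table 3 marks no solicited recording at Day 14.

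On windows, the ±7 looks like the vaccination window carried forward in study days. Visit 13 is also printed as Day 44 ± 7, and Table 4 tightens it to 14 ± 3 from vaccination. This is plausible, but nothing does the same for Visits 12 and 18. A reader might combine the vaccination and visit windows and get 30 − 37 = −7 to 44 − 23 = +21 days. The documents do not support that range: a post-vaccination visit cannot precede its vaccination, and the next visit is due by day 17.

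On the way of asking, Table 5 requires a grade for each listed symptom, including grade 0. Baseline solicited general symptoms are recorded before each vaccination, and 10.2 asks about medical advice symptom by symptom. These rules partly offset 10.1.3. It would also go too far to say that solicited and unsolicited counts become interchangeable, because 10.1.5 separates them by symptom list and onset and 10.1.3 uses separate CRF pages.

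Finally, the loss may be small. Section 4.3.7 reports that most solicited symptoms in Gambian adults given the same adjuvant with another antigen were short-lived (4 days). For an occurrence endpoint, Day 7 then adds mainly later onsets. That is fair. The Mozambique result in the same section says less, because its solicited follow-up was itself only 4 days.

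**Conclusion.** The three conflicts are in the current text and concern a primary endpoint.

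- **Visit 6.** The list conflicts with 10.1.2, 12.1 and Table 3: 4/5/5 solicited contacts against 5/5/5.
- **Windows.** Those for Visits 12 and 18 are not tied to the vaccination date. They allow post-vaccination days 0 to 14 when vaccination falls on the nominal day.
- **Way of asking.** Section 10.1.3 conflicts with the glossary.

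The supportable consequence is that symptoms could be captured differently after vaccination 1 than after vaccinations 2 and 3, and that the open question could lower capture in all groups. A reader might infer uneven capture between the 25 µg, 50 µg and rabies arms. The documents do not support that, because all arms share one visit schedule and one set of rules. The Fisher tests in 12.5.3 compare study groups, and no test between vaccinations is planned.

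Days 0 to 3 are untouched by the first two conflicts. The loss is conditional on which text staff follow, and its size cannot be computed from the documents. The trial is descriptive and claims no power, so no design figure changes. This is a consistency correction to make before enrolment. It does not put the design in doubt.

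**What to change.** - **7.1.6, Visit 6:** add solicited-symptom recording and an injection-site examination line, to agree with Table 3 and with Visits 12 and 18.
- **Table 4:** add rows for Visit 2 to 6, Visit 8 to 12 and Visit 14 to 18, with one common window counted from the vaccination date, and change 7.1.6 to match. The ±1 and ±7 must be reconciled. The sponsor should choose the width and check it against the review in 7.1.5 and the SMC calls in 15.4.
- **10.1.3:** state that the symptoms in 10.1.4 are asked item by item at each visit where solicited recording is due, and keep the open question for unsolicited events, in line with the glossary.

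The cost is protocol and CRF wording and a line in staff training. The visits and staff are already planned, and neither the sample size nor the analysis changes.
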